3. SCHEDULE OF EVALUATIONS

Visit Number	Screen	Visit 1	Contacts 1 and 2	Visit 2	Visit 3	Visit 4	Visit 5	Visit 6	Contact 3
Trial Timeline	Day -21 to 0	Day 0	Days 1 and 2 ¹	Day 3	Day 7	Day 42	Day 180 ¹	Day 360 ¹	Days 720 ¹
Visit/Contact Window (Days)	N/A	N/A	+/- 0	+/- 1	+/- 1	+/- 4	+/- 28	+/- 28	+/- 28
Informed Consent	X								
Inclusion/Exclusion	X	X							
Medical History	X								
Interim Medical History		X	X	X	X	X	X	X	X
Concomitant Medications	X	X	X	X	X	X	X	X	
Physical Examination	X								
HIV and Illicit Drug Test	X								
Physical Assessment: Vital Signs ² /Node Check		X		X	X	X	X	X	
Safety Labs (CBC, Blood Chemistry, PT, PTT, Urinalysis) ^{2,3}	X	X			X	X			
Surgical Treatment		X							
Surveillance (30 minutes)		X							
CT	X	X				X	X	X	
Diary Cards Distributed/Collected		X			X	X	X	X	X
Unsolicited Adverse Events		X	X	X	X	X	X	X	X

¹ Subjects will be contacted at Days 1 and 2, Days 42 and at 6 months, 1 year, and 2 years with a scripted telephone contact for safety follow-up and scheduling.

² Vital signs and laboratory values will be evaluated using the appropriate FDA draft guidance.

³ Any abnormal laboratory result arising post-administration, and of moderate or greater severity, will be followed until results return to baseline value or for the duration of safety follow-up.

4. LIST OF ABBREVIATIONS

°C	Degrees Celsius
°F	Degrees Fahrenheit
AE	Adverse event
ALT	Alanine aminotransferase
AST	Aspartate aminotransferase
ATP	According to protocol
BUN	Blood urea nitrogen
CBC	Complete blood count
CDC	Centers for Disease Control
CFR	Code of Federal Regulations
CI	Confidence interval
CPE	Cytopathic effects
CPK	Creatine phosphokinase
CRF	Case Report Form
DIC	Disseminated intravascular coagulation
dL	Deciliter
DNA	Deoxyribonucleic acid
ER	Emergency room
FDA	Food and Drug Administration
GCP	Good Clinical Practice
HIV	Human Immunodeficiency Virus
ICH	International Committee on Harmonization
IND	Investigational New Drug
IRB	Institutional Review Board
ITT	Intention to treat
IV	Intravenously
MedDRA	Medical Dictionary for Regulatory Activities
mEq	Milliequivalents
mL	Milliliter
mm	Millimeter
mM	Millimolar
N/A	Not applicable
ND	Not determined
NP	Nasopharyngeal
OTC	Over the counter
PCR	Polymerase chain reaction
PIN	Participant identification number
PRBC	Packed red blood cells
PT	Prothrombin time
PTT	Partial thromboplastin time
rbc/hpf	Red blood cells per high power field
SAE	Serious adverse event
SOP	Standard operating procedure
SRC	Safety Review Committee
ULN	Upper limit of the normal range
v/v	Volume by volume
WBC	White blood cell
WHO	World Health Organization
w/v	Weight by volume
mg	microgram
mL	microliter

5. INTRODUCTION

5.1 Investigational Product Description

[figure not shown]
The B-247 Cranial Bone Graft Implant is an experimental device which consists of plasmid DNA (pln.247-pBI, 200 $\mu\text{g}/\text{ml}$ of implant volume) for transient expression of human perlecan domain 1 with 100 $\mu\text{g}/\text{ml}$ rhBMP-2 in a gelatin/tricalcium phosphate scaffold for cranial bone regeneration. The product is provided as a pliable solid single-phase unit consisting of 80% bioactivated tricalcium phosphate (TCP) crystals 200-600 μm particle size, evenly distributed within a 20% cross-linked gelatin polymer. The implant is bioactivated by incorporating plasmid DNA lipoplexes and rhBMP-2 in 1% sucrose excipient, then lyophilizing the loaded implant to a final concentration of 200 $\mu\text{g}/\text{ml}$ of implant of pln.247-pBI plasmid and 100 $\mu\text{g}/\text{ml}$ of implant of rhBMP-2. Plasmid lipoplexes are derived from incubating pln.247-pBI plasmid with Lipofectamine 2000 in a 2:1 ratio for 30 minutes. Sucrose, plasmid, rhBMP-2, Lipofectamine 2000, TCP crystals, and gelatin are each manufactured separately according to cGMP and combined under sterile conditions in a clean room.

- rhBMP-2 is marketed in the US as a component of the InFuse™ device kit by Medtronic, Inc. This kit was approved under PMA P050053 on 03/13/2007. The rhBMP-2 is manufactured in a human CHO cell line.
- Tricalcium phosphate crystals are marketed in the US as Osteogen by Implants. This product was approved under 510(k) Premarket Notification on 5/31/1995.
- Sucrose and gelatin are common excipients and are purchased cGMP quality.
- Lipofectamine 2000 is purchased from Life Technologies as a cGMP grade cationic lipid.
- The pln.247-pBI expression plasmid is manufactured by Aldevron in a cGMP manner derived from *E. coli* fermentation.

5.2 Regenerating Bone in Large Critical Size Defects

Mature bone consists of inorganic calcium phosphate (70% wt.), proteins such as collagen and proteoglycans (25% wt.), water (4% wt.) and of course cells, blood vessels, and neurons (1% wt.). Normal bone is constantly remodeling, or turning over at a rate of up to 15-35%/year in some areas. Therefore, the therapeutic approach to bone regeneration must be considered in this light, and, indeed, bone growth, (apposition) is always accompanied by some degree of bone loss (resorption) in a process that is cyclic. It is the balance between bone apposition and resorption that dictates the state of the bone in a given region of the body.

New bone growth is complex and requires bone forming cells called osteoblasts which derive from the surfaces of existing bone or from pluripotent circulating cells (adult stem cells) that originate in the marrow. The normal adult process of bone apposition occurs on the surfaces of existing bone structure where bone-resorbing cells called osteoclasts remove a layer of bone, and osteoblasts subsequently deposit new bone matrix. The cycle favors osteoblast activity in periods of net apposition.

Regenerating bone in a space where bone surfaces and a source of migrating osteoblasts are absent or distant, such as an attempt to rebuild the jaw to support implants in a patient whose jaw bone has resorbed severely or has been otherwise lost to disease or trauma, one must supplement the site with an osteoinductive graft material. Osteoinduction is the process whereby bone formation is induced beyond the normal bone-regenerating capacity of the site. By seeding bone defects with fresh bone from another source in the body, or by actively promoting 1) migration of pre-osteoblasts and osteoblasts, 2) differentiation (maturation) of the circulating adult stem cells into pre-osteoblasts then osteoblasts, and 3) proliferation (multiplication) of osteoblasts and pre-osteoblasts throughout the wound or graft, new bone can be regenerated before a mature non-mineralizing connective tissue occupies the space.

All three of these processes – migration, differentiation, and proliferation - are enhanced by the activity of a class of proteins called growth factors. Growth factors that are thought to have some role in bone formation include the bone morphogenetic proteins (BMP) 2 and 7, platelet derived growth factor (PDGF), fibroblast growth factor (FGF), insulin growth factor (IGF), and vascular endothelial growth factor (VEGF). Of these and other known growth factors, BMP-2 may hold the most potential for osteoinduction as it is known to promote differentiation of circulating stem cells into pre-osteoblasts and away from other non-bone forming cell types. Other growth factors, such as FGF-2, have a known ability to enhance the proliferation of osteoblasts and pre-osteoblasts, so they too have a potential supporting role in effective osteoinduction.

Augmenting growth factor activity is critical in treating larger bone defects that have an inherently limited potential to regenerate bone because these three processes cannot occur extensively and rapidly enough throughout the larger bone defect. The addition of growth factors alone, however, is not enough.

Bone is not all mineral, as pointed out above, and actually begins as a soft organ consisting of protein aggregates such as the collagens, with other bone-specific proteins, and proteoglycans. As this non-calcified matrix (termed osteoid) is laid down by the osteoblasts, the bone-specific nature of the osteoid allows the gradual accumulation of mineral and hardening of the osteoid into bone.

Proteoglycans were long considered only structural components of tissues such as bone but now are now known to have very important biological activities. Proteoglycans are composed of a protein core, to which is attached long and diverse co-polymeric chains consisting of hexuronic acid and hexosamine sugars. These oligosaccharides are known as glycosaminoglycans (GAGs) and vary in chain length and charge, due to the addition of sulfate groups to various positions on the constituent monosaccharides. The class of heparan sulfate proteoglycans are now being focused on for their role in tissue and cell regulation, particularly angiogenesis, growth factor activation, and wound healing.

Perlecan, originally named heparan sulfate proteoglycan-2, is an important component of all basement membranes and, with three potential sites for heparan sulfate GAG attachment, is an excellent example of a regulatory biomolecule. A body of evidence in the literature exists demonstrating a role for heparan sulfate proteoglycans, and perlecan in particular, in cell adhesion, cell proliferation, cell differentiation, and cell migration, all of which are crucial to osteoinduction.

The B-247 Cranial Bone Graft Implant generates a heparan sulfate proteoglycan that tightly binds FGF-2 or BMP-2 (0.3 nM estimated K_D) and significantly augments BMP activity in an osteoblast mineralization assay (or FGF-2 in a proliferation assay). Classic growth factor/receptor interaction mechanisms suggest that the heparan sulfate chains co-activate growth factors by promoting receptor dimerization through binding interactions between the growth factors and the glycosaminoglycans.

5.3 Advantages of the B-247 Cranial Bone Graft Implant

Bone grafts using bone harvested from elsewhere in the patient (autogenous), while effective, can create lasting and debilitating pain at the site of harvesting, and is naturally limited. Bone graft substitutes are necessary. However, products that use cadaver bone (allografts) have the potential for disease transmission and are not sufficiently effective, only slightly more effective than inert synthetic bone graft materials such as the calcium phosphates, which are used in approximately 30% of cases. Newer products combine growth factors with synthetic bone graft substitutes, constituting an approximately 2-3 billion dollar market (Windhover Information).

The growth factor called platelet derived growth factor, or PDGF, is available for periodontal and related oral surgery procedures in a device kit and is used in approximately 10-20 % of cases, despite its lack of clearly defined superiority.

Another biologically enhanced synthetic bone grafting gel, named Emdogain, is available for periodontal or related oral surgical use. This gel is a complex mix of porcine tissue that also brings the potential for growth factor activity to the bone defect and is also used in approximately 10-20 % of cases for periodontal therapy.

Currently, there are two BMP products on the market. One is marketed by Medtronic through its branded product InFuse®. InFuse® uses BMP-2. Another BMP, BMP-7, is used in OP-1® developed by Stryker. There are, however, inherent problems with the current use of BMPs because dangerously high levels of the growth factor are required for only moderate efficacy (moderate because of the lack of a necessary heparan sulfate co-activator that is the B-247 technology). Only InFuse® is approved for craniofacial use.

Added to the safety issues there is one of cost. The ability to reduce the BMP content in any product, by a factor of as much as thirty, could have a demonstrable affect on usage and profitability. Currently, many

clinicians say that in spite of the relative effectiveness of these products, the price is simply too high. This is especially true in the case of periodontal and oral surgeries where reimbursement can be limited. InFuse® is used in approximately 10% of the craniofacial bone graft cases, though in spinal regeneration, InFuse® is used in more than 25% of the cases.

An additional concern is that InFuse® only allows the placement of a sponge which retains the rhBMP-2 for a very short period of time and has very little structural integrity or adaptability for irregular wounds. The B-247 Cranial Bone Graft Implant overcomes each of these shortcomings. First, the TCP crystals tightly bind and gradually release the pln.247-pBI plasmid and the rhBMP-2 so the risk of local seroma or systemic toxicity within 3 days after placement are reduced. Second, the cross-linked gelatin scaffold retains the crystals so the biologicals remain where placed. Third, the cross-linked gelatin scaffold allows the graft to be molded into the wound and is adaptable to irregular wounds. Fourth, the cross-linked gelatin scaffold is not a putty, as used by Stryker, but is a porous scaffold for immediate cell infiltration.

The clinical objective is to grow new bone where bone has been lost. In doing so, the **first requirement** is that space must be filled with a material (liquid, gel, solid, particles, or porous polymer) that allows/promotes cellular infiltration immediately. The **second requirement** is that the material should retain and protect the biologics (growth factor and co-activator) from pre-mature release in the first few days since the early wound is highly inflammatory. The material should gradually release the majority of biologic load between 4 and 14 days for most effect during the beginning of the regenerative phase.

The B-247 Cranial Bone Graft Implant generates a heparan sulfate proteoglycan that tightly binds FGF-2 or BMP-2 (1 nM estimated kD) and significantly augments BMP activity in an osteoblast mineralization assay (or FGF-2 in a proliferation assay). Classic growth factor/receptor interaction mechanisms suggest that the heparan sulfate chains co-activate growth factors by promoting receptor dimerization through binding interactions between the growth factors and the glycosaminoglycans.

5.4 Advantages of Plasmid DNA Pro-Drug Therapy

Pln.247-pBI is a plasmid DNA pro-drug that, when incorporated by the resident cells at the site of administration, results in the generation of recombinant proteoglycan as an *in situ* therapeutic, with crucial post-translational modifications to the glycosaminoglycan side chains that can be dictated by the wound environment by this method of delivery.

5.5 Rationale for Phase I Study of B-247 Cranial Bone Graft Implant

Agenta has performed a series of *in vitro* experiments clearly demonstrating the ability of the recombinant that is expressed by pln.247-pBI plasmid (rPln.247) to augment growth factor activities.

In vivo Safety Data: doses of pln.247 from 40 µg/ml to 360 µg/ml graft volume have shown no signs of toxicity, or general morbidity. While TCP stimulated BMP-2 associated intramembranous bone formation that was juxta-proximal to the particles, (see (2)), and new bone that was contiguous with the maxilla, remnants of TCP particles remain embedded within the new bone for at least 12 weeks. The histopathology on >200 maxillary bone defects treated with doses ranging from 40 µg/ml to 360 µg/ml graft volume show no local pathology or acute bone resorption attributable to biologics. The CBC and clinical chemistry safety data showed hematology and clinical chemistry values within normal limits for aging rats.

Conclusion

- pln.247 plasmid more than doubles the dose-effectiveness of BMP-2 osteogenic activity for *in vivo de novo* bone generation
- B-247 formula of TCP, BMP-2, and pln.247 plasmid is superior to OsteoGen TCP bone graft
- B-247 provides more than 5 times as much maxillary ridge augmentation than InFuse™ using ≈1/50th of the BMP-2 dose
- B-247 formula generated new bone with 4 fold greater density than new bone generated by InFuse™.
- B-247 did not cause osteonecrosis in the first 3 weeks post-implant as did InFuse™.

There is no previous human experience with plasmid DNA augmentation of the perlecan domain 1. There is a large body of data regarding the use of 1.5 mg/ml rhBMP-2 in craniofacial and orthopedic bone regeneration (InFuse®) and for rhBMP-7 (OP-1®). The data suggest that the dose of rhBMP required for the partial clinical efficacy is almost too great and poses a poor risk/benefit ratio. Therefore, the trial of an experimental product such as B-247 Cranial Bone Graft Implant, which has the potential to significantly lower the dose of rhBMP-2 while improving the efficacy with the safe addition of a relatively low level of plasmid DNA would be of great value to the field of medicine.

Subsequent clinical studies will evaluate the safety and efficacy of the B-247 Cranial Bone Graft Implant in direct comparison to other clinically accepted methods for treatment.

6. OBJECTIVES

6.1 Primary Objective

The primary objective is to evaluate the safety of the B-247 Cranial Bone Graft Implant when administered to adults with cranial bone defects in medical need of repair.

6.2 Secondary Objective

The secondary objective is to evaluate the efficacy of the B-247 Cranial Bone Graft Implant in the regeneration of bone in existing cranial bone defects.

7. STUDY DESIGN

7.1 Study Overview

This is a single center, unblinded, safety and efficacy study.

A total of 12 subjects will be enrolled.

All 12 subjects will receive the B-247 Cranial Bone Graft Implant.

Enrollment will begin with 3 subjects enrolled at a rate of no more than one subject per week. The second, and third subjects will only be treated with the experimental device if stopping rules (see Section 14.3) are not met and other safety concerns are absent. Following review of Day 7 safety data for each of the first 3 subjects, the SRC will determine whether to open enrollment to the remaining 9 subjects or to discontinue enrollment. The SRC will review the occurrence of AEs weekly, with 24 hour reporting for SAEs. Stopping rules are described in full in Section 14.3.

Safety will be assessed in all participants. Each participant will be requested to record solicited AEs daily for 2 years after their device placement using study diary cards. Additionally, unsolicited adverse events will be collected immediately following surgical device placement through two years via telephone contacts and at clinic visits. Serious adverse events (SAEs) will be collected throughout the 2 year period of safety surveillance.

Safety evaluation will include hematologic and biochemical toxicity evaluation.

Blood and urine samples will be collected at screening (Day -21 to -1), on Day 0 prior to administration of the device, and again on Days 7, and 42 to measure the effects of device on blood chemistry, urinalysis, and hematology. The urine and blood samples obtained on Day 0 will be used for the baseline comparison.

Subjects will be asked to undergo a physical examination at screening (Day -21 to -1) and a physical assessment including vital signs, lymph node exam, and symptom directed exams at all clinic visits following enrollment (Days 0, 3, 7, 42, 180, and 1 year).

Telephone contacts will occur on the first two days after surgery (Days 1, 2) for study staff follow-up on possible adverse events. In addition, telephone contacts will be made after two years to document the occurrence of SAEs and the resolution of AEs ongoing at the one-year visit.

The overall safety assessment of the device will be based on the incidence of local and systemic reactogenicity, the incidence of changes to laboratory parameters relative to baseline values, and solicited and unsolicited adverse events.

Information will be collected on the osteoinduction associated with the device. A CT scan will be performed on each subject at baseline prior to placement of the device, then again at day 42, day 180, and at one year.

7.2 Trial Center

This trial will be conducted throughout the UAB Health System through the UAB Dept. of Neurosurgery at the University of Alabama, Birmingham under the direction of [name].

7.3 Reference Committees

A Safety Review Committee (SRC) will be utilized throughout this trial. The SRC is composed of the Principle Investigator, Agenta’s Medical Monitor, and a third member appointed by the Principle Investigator. The SRC will assess the progress of the clinical trial weekly and will determine whether to continue, modify, or stop the trial at protocol-specified intervals. The safety data review procedure used by the SRC is described in Section 9.3. The SRC is responsible for the clinical evaluation of the safety of the experimental bone graft device based on medical and ethical considerations. A detailed description of the responsibilities of the SRC is provided in Section 14.

8. STUDY POPULATION

8.1 Inclusion Criteria

1. Males, 19 to 59 years of age, in need of cranial bone repair.
2. Subjects must provide written informed consent (attached to grant).
3. Subjects must be willing to participate through study completion.
4. Subjects must be willing to undergo CT examination at day 42, 180, and 360 after surgery for safety and efficacy analyses.
5. Screening Laboratory Inclusion Criteria (normal ranges determined by institutional criteria):

Hematology	CBC (hemoglobin, hematocrit, WBC count, Differential, Platelets)
Chemistry*	ALT, AST, alkaline phosphatase
	Creatinine
	Blood Urea Nitrogen (BUN)
	Sodium
	Potassium
	Chloride
Urinalysis	Bicarbonate
	Urine glucose
	Urine protein

1. Female, due to the long-term nature of the study and potential complications or risks pregnancy may introduce.
2. History of metabolic bone disease of any type, including osteoporosis.
3. Any previous cranial surgery
4. Any illicit drug use.
5. HIV positive at screening, due to the long-term nature of the study and potential complications or risks this may introduce.
6. Known or suspected malignancy, leukemia, or lymphoma. Malignancy not excluded: A participant with a surgical excision and subsequent observation period that in the investigator's estimation has a reasonable assurance of sustained remission and/or is unlikely to recur during the period of the study.
7. Immunosuppressed, including altered or compromised immune status as a consequence of disease or treatment with systemic corticosteroids (including inhaled or intranasally-administered drugs), alkylating drugs, anti-metabolites, radiation, or other immunosuppressive therapies.
8. Receipt of any investigational drug in the past 30 days.
9. Known Diabetes mellitus.
10. Hypertension that is not well controlled: Blood Pressure \geq 150/100 (either or both values) at screening or enrollment.
11. Any medical, psychiatric, or social condition, or occupational or other responsibility that, in the judgment of the investigator, would interfere with, or serve as a contraindication to, protocol adherence, assessment of safety or reactogenicity, or a participant's ability to give informed consent.

8.3 Prior and Concomitant Therapy

Notwithstanding above exclusions (section 8.2), standard medical protocol for pre-existing medications and post-operative management will apply, including post-operative instructions by the physician.

Participants will be advised that they are not to receive other investigational products (drug or vaccine) for 180 days post vaccination.

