Subjects will receive compensation for their time and effort at the completion of each clinic visit beginning with the 6 week follow-up.

Data and Safety Monitoring: The first three subjects will be enrolled at a rate of no more than one subject per week. After review of the 7 day safety data for each of the first 3 subjects, the Safety Review Committee (SRC) will recommend either to open enrollment for the remaining subjects or to discontinue enrollment. The SRC will review the occurrence of AEs weekly, with 24 hour reporting for SAEs. Stopping rules will be defined in the protocol.

Monitored Parameters:

Safety:

- Hematology, blood chemistry, urinalysis
- Vital signs and physical assessments
- Unsolicited and solicited adverse events (clinic visits, diary cards and telephone contacts)
- Follow-up safety surveillance through 2 years

Bone Regeneration:

- CT analysis

Endpoints:

Safety:

- Incidence of local adverse events including ectopic bone formation if any
- Incidence of systemic adverse events
- Incidence of changes to laboratory parameters relative to baseline values

Bone Regeneration:

- The proportion of subjects at Day 42 and 180 and 360 with evidence of mineralized bone regeneration at the site of the original cranial defect relative to baseline (Day 0)
- The percentage of bone regeneration in the original cranial defect at Day 42 and 180 and 360 relative to 0% at baseline (Day 0)

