- e. Obtain blood samples (10 mL + 5 mL) and urine sample for clinical laboratory assessments.
- f. Obtain blood sample (4 mL) for PT and PTT tests.
- g. Collect and discuss diary card / distribute new diary card.
- h. Record AEs and SAEs.
- i. Set up appointment for Visit 4 (Day 42).

Visit 4 (Day 42)

- a. Confirm that the subject wishes to remain in the trial.
- b. Obtain interim medical history.
- c. Review diary card with subject.
- d. Record concomitant medication.
- e. Perform physical assessment (vital signs, lymph node exam, and symptom directed exam).
- f. Obtain blood samples (10 mL + 5 mL) and urine sample for clinical laboratory assessments.
- g. Obtain blood sample (4 mL) for PT and PTT tests.
- h. Record AEs and SAEs.
- i. Obtain radiographs and CT images of experimentally treated cranial defect.
- j. Set up appointment for Visit 5 (Day 180).

Visit 5 (Day 180)

- a. Confirm that the subject wishes to remain in the trial.
- b. Obtain interim medical history.
- c. Review diary card with subject.
- d. Record concomitant medication.
- e. Perform physical assessment (vital signs, lymph node exam, and symptom directed exam).
- f. Record AEs and SAEs.
- g. Obtain CT images of experimentally treated cranial defect.
- h. Set up appointment for Visit 6 (Day 360).

Visit 6 (Day 360)

- a. Confirm that the subject wishes to remain in the trial.
- b. Obtain interim medical history.
- c. Review diary card with subject.
- d. Record concomitant medication.
- e. Perform physical assessment (vital signs, lymph node exam, and symptom directed exam).
- f. Record AEs and SAEs.
- g. Obtain CT images of experimentally treated cranial defect.
- h. Set up appointment for Contact 3 (Day 730).

Telephone Follow-up (Day 730)

Study personnel (study coordinator or other personnel assigned by the investigator) will contact the participant to collect information on ongoing, previously recorded adverse events and new or ongoing SAEs. Reminder postcards will be mailed to each participant approximately one month prior to this contact. Study personnel will contact the participant by telephone approximately two weeks in advance of the follow-up target date to schedule a time for the telephone contact. During the telephone conversation, study personnel will collect interim medical history as well as update contact information.

Contact 3 (Day 730)

- a. Confirm that the subject wishes to remain in the trial.
- b. Obtain interim medical history.
- c. Record AEs and SAEs.

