13.2 Variables and Timepoints of Measurement

13.2.1 Safety Variables

In-clinic safety evaluation on Days 0, 3, 7, 42, 180, and 360 will be graded for severity and relationship to the study agents and will include:

- a) Rates of SAEs and their relationship to device placement, through 2 years of long-term follow-up.
- b) Rates of local or systemic solicited AEs and their categories (mild, moderate and severe), through Day 360 ± 28 days.
- c) Rates of reported unsolicited AEs, through Day 360 ± 28 days.
- d) Hematologic and biochemical toxicity evaluation following device placement.

Osteogenicity will be evaluated using radiographs and CT scans obtained from participants on Day 0 (baseline, pre-implantation), Day 42 (± 7), 6 weeks after device placement), and Day 180 (± 14) 6 months after device placement).

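### The restriction on other investigational products has no valid start, an unclear scope, and lapses about 180 days before the Day 360 bone endpoints

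*Protocol*

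**What the plan says.** Section 8.3 holds the only restriction on other investigational products after implantation: participants are advised that they are "not to receive other investigational products (drug or vaccine) for 180 days post vaccination". The one related entry criterion, exclusion 8 in Section 8, looks backwards and names drugs only: "Receipt of any investigational drug in the past 30 days".

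The product under test is not a vaccine. Section 5.1 states: "The B-247 Cranial Bone Graft Implant is an experimental device which consists of plasmid DNA".

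The horizons that the restriction has to serve are these:

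- **Bone endpoints (Section 2, Endpoints).** "The proportion of subjects at Day 42 and 180 and 360 with evidence of mineralized bone regeneration", and "The percentage of bone regeneration in the original cranial defect at Day 42 and 180 and 360 relative to 0% at baseline".
- **Imaging.** Section 9.1 lists for Visit 6 (Day 360): "Obtain CT images of experimentally treated cranial defect". The Section 3 schedule gives this visit a window of ±28 days.
- **Analysis (Section 13.1.1).** One full analysis follows the Day 180 data and a second follows the Day 360 data.
- **Safety (Section 13.2.1).** SAEs run longest: "Rates of SAEs and their relationship to device placement, through 2 years of long-term follow-up". Solicited and unsolicited AE rates are taken to Day 360 ± 28 days.
- **Recording (Sections 3 and 9.1).** Concomitant medications are recorded at visits up to Visit 6 but not at Contact 3. Contact 3 does take interim medical history.

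**The concern.** The sentence in Section 8.3 reads as if carried over from a vaccine protocol, and it does not fit this trial in three respects: when the restriction starts, which products it covers, and how long it lasts.

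Length matters most for the statistics. A subject could follow Section 8.3 exactly, receive another experimental product after Day 180, and still contribute to the Day 360 bone result. All 12 subjects receive B-247 and there is no comparator, so no control group could show what the other product contributed. The Day 360 finding in that subject could not be assigned to the implant with confidence.

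For safety, Section 10.2 separates a probable from a possible relation by whether an alternative cause is apparent. A late SAE is harder to place if nobody has asked about other investigational exposure.

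This is not a matter to leave to an analysis plan. What subjects may receive, and what they are asked about, is fixed by the protocol, and an analysis cannot recover information that was never collected.

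**Working it through.** The protocol gives no figure for use of other investigational products, so there is no stated result to reproduce. The check is a comparison of dates, taking Day 0 as device placement.

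**1. Start.** Read literally, the 180 days run from a vaccination, which never occurs. The steps below assume that device placement was meant, so the restriction ends at Day 180.

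**2. Scope.** The general term in Section 8.3 is investigational products; the parenthesis then lists drugs and vaccines. B-247 is itself called an experimental device (Sections 5.1 and 12.1). Nothing else in the protocol says whether devices or biologics are included.

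**3. Gap before the Day 360 CT.**
- Nominal: 360 − 180 = 180 days, and 180/360 = 50% of the interval from placement to that CT.
- Earliest CT in the window: 360 − 28 = Day 332; 332 − 180 = 152 days.
- Latest CT in the window: 360 + 28 = Day 388; 388 − 180 = 208 days.

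**4. Day 180 CT.** The protocol gives two windows.
- Section 3, ±28 days: latest CT at 180 + 28 = Day 208, which is 28 days after the lapse.
- Section 13.2.1, ±14 days: latest CT at 180 + 14 = Day 194, which is 14 days after the lapse.

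**5. Safety follow-up after the lapse.**
- SAEs, last contact at Day 720 (Sections 3 and 11.1): 720 − 180 = 540 days; 540/720 = 75.0%.
- SAEs, last contact at Day 730 (Sections 9.1 and 10.1): 730 − 180 = 550 days; 550/730 = 75.3%.
- Solicited and unsolicited AE rates, to Day 360: 360 − 180 = 180 days, or 208 with the window.

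**6. Effect of one subject on the Day 360 proportion.** With all 12 evaluable, 1/12 = 8.3 percentage points. This is a ceiling per subject. It is reached only if the other product changes that subject from non-responder to responder or the reverse; otherwise the effect is zero. With fewer evaluable subjects the step is 1/n, for example 1/10 = 10 points.

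**7. What would be detected.**

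| Period | Investigational drug | Investigational device or graft |
|---|---|---|
| Day 180 to Day 360 | Concomitant medications at Visits 5 and 6: recorded, not prevented | Not clearly a medication; interim history or CT may reveal it |
| Day 360 to 2 years | No medication record at Contact 3; interim history only | Interim history only |

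**The case against.** The case on the other side has real weight.

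- **Detection.** A reader might infer that later exposure would go unseen. The protocol does not support that. Medications are recorded through Visit 6, interim history is taken at every later contact, Diary Card #5 runs to the 2-year contact, and the treated site is imaged at Days 42, 180 and 360. A second graft at the site would be unlikely to pass unnoticed. What stands is that recording does not prevent confounding, and that no question at Contact 3 asks specifically about investigational products.
- **Attribution.** A reader might infer that, without a control, every AE counts against B-247. Sections 10.1 and 10.2 require a judgement of relationship and include an unrelated category. Attribution is harder here but not automatic.
- **Scope.** A reader might infer that investigational devices are permitted from Day 0. The general term could include them, and the protocol elsewhere calls B-247 a drug product (Section 12.4). The scope is ambiguous, not clearly open.
- **Horizon.** Day 180 is a milestone in its own right: Section 9.4 defines normal completion by it, the first full analysis follows it, and Section 13.2.1 lists it as the last osteogenicity timepoint. That explains the figure. It does not cover the Day 360 endpoints, which remain in the synopsis, the schedule and the analysis plan of Section 13.1.1.
- **Size.** The 75% in step 5 is follow-up time outside the restriction, and it concerns SAEs. It is not a share of contaminated data, and the planned AE rates stop near Day 360.

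**Conclusion.** The point holds as a mismatch between a rule and the endpoints it should protect. Section 8.3 has no valid start in this trial, leaves devices and biologics unclear, and, on the charitable reading, lapses 180 days (152 to 208) before the Day 360 CT. In a single arm of 12, another investigational product taken in that gap could be confounded with B-247.

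This rests on two assumptions: that device placement is the intended start, and that the synopsis endpoints at Day 360 stand despite their absence from the osteogenicity timepoints in Section 13.2.1.

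The direction and size of any bias are unknown. The protocol gives no rate of co-exposure, and 8.3 points is a ceiling for one subject, not an estimate. It would also go too far to call the Day 180 CT unprotected: only a late scan is exposed, by 14 or 28 days depending on which window applies. For SAEs to 2 years the gap is narrower still, being the lack of a direct question at the last contact. The change is worth making because it is cheap; the trial does not fail without it.

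**What to change.** Reconcile Section 8.3 with the synopsis endpoints, the Section 3 schedule, Section 9.1 and Sections 13.1.1 and 13.2.1, so that the restriction:

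1. starts at device placement;
2. covers any investigational product, naming drug, biologic, device and vaccine;
3. runs through the last bone-endpoint CT, including its window.

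Settle the Day 180 imaging window (±28 or ±14 days) and the omission of Day 360 from Section 13.2.1 in the same amendment, since the end of the restriction depends on which imaging timepoints count.

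At Contact 3, add one question on any investigational product or further cranial implant received since Day 360, and record the answer. About 360 of 720 days would still lie beyond a restriction ending at Day 360 (720 − 360 = 360). The question lets late SAEs be judged against known exposure without a longer restriction.

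The cost is protocol and consent wording and one item in a call that already takes place. The downside falls on subjects, who are asked to stay out of other trials for about six months longer (360 − 180 = 180 days, or up to 208 with the window). No sample size or power figure changes.
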